### Assessment of Causality

- The investigator is obligated to assess the relationship between study treatment and each occurrence of each AE/SAE.
- A "reasonable possibility" of a relationship conveys that there are facts, evidence, and/or arguments to suggest a causal relationship, rather than a relationship cannot be ruled out.
- The investigator will use clinical judgment to determine the relationship.
- Alternative causes, such as underlying disease(s), concomitant therapy, and other risk factors, as well as the temporal relationship of the event to study treatment administration will be considered and investigated.
- The investigator will also consult the Investigator's Brochure (IB) and/or Product Information, for marketed products, in his/her assessment.
- For each AE/SAE, the investigator **must** document in the medical notes that he/she has reviewed the AE/SAE and has provided an assessment of causality.
- There may be situations in which an SAE has occurred and the investigator has minimal information to include in the initial report to GSK. However, **it is very important that the investigator always make an assessment of causality for every event before the initial transmission of the SAE data to GSK.**
- The investigator may change his/her opinion of causality in light of follow-up information and send an SAE follow-up report with the updated causality assessment.
- The causality assessment is one of the criteria used when determining regulatory reporting requirements.

### Follow-up of AE and SAE

- The investigator is obligated to perform or arrange for the conduct of supplemental measurements and/or evaluations as medically indicated or as requested by GSK to elucidate the nature and/or causality of the AE or SAE as fully as possible. This may include additional laboratory tests or investigations, histopathological examinations, or consultation with other health care professionals.
- If a participant dies during participation in the study or during a recognized follow-up period, the investigator will provide GSK with a copy of any post-mortem findings including histopathology.
- New or updated information will be recorded in the originally completed CRF.
- The investigator will submit any updated SAE data to GSK within 24 hours of receipt of the information.

## Reporting of SAEs to GSK

### SAE Reporting to GSK via Electronic Data Collection Tool

- The primary mechanism for reporting SAE to GSK will be the electronic data collection tool (e.g., InForm).
- If the electronic system is unavailable for more than 24 hours, then the site will use the paper SAE data collection tool (see next section).
- The site will enter the SAE data into the electronic system as soon as it becomes available.
- The investigator or medically-qualified sub-investigator must show evidence within the eCRF (e.g., check review box, signature, etc.) of review and verification of the relationship of each SAE to IP/study participation (causality) within 72 hours of SAE entry into the eCRF.
- After the study is completed at a given site, the electronic data collection tool will be taken off-line to prevent the entry of new data or changes to existing data.
- If a site receives a report of a new SAE from a study participant or receives updated data on a previously reported SAE after the electronic data collection tool has been taken off-line, then the site can report this information on a paper SAE form (see next section) or to the medical monitor or SAE coordinator by telephone.
- Contacts for SAE reporting can be found in the study procedures manual.

## 12.5. Appendix 5: Contraceptive Guidance and Collection of Pregnancy Information

### Definitions

#### Woman of Childbearing Potential (WOCBP)

A woman is considered fertile following menarche and until becoming post-menopausal unless permanently sterile (see below)

#### Women in the following categories are not considered WOCBP

1. Premenarchal
2. Premenopausal female with ONE of the following:
  - Documented hysterectomy
  - Documented bilateral salpingectomy
  - Documented bilateral oophorectomy
3. Postmenopausal female
  - A postmenopausal state is defined as no menses for 12 months without an alternative medical cause. A high follicle stimulating hormone (FSH) level in the postmenopausal range may be used to confirm a postmenopausal state in women not using hormonal contraception or hormonal replacement therapy (HRT). However, in the absence of 12 months of amenorrhea, a single FSH measurement is insufficient.
  - Females on HRT and whose menopausal status is in doubt will be required to use one of the non-hormonal highly effective contraception methods if they wish to continue their HRT during the study. Otherwise, they must discontinue HRT to allow confirmation of postmenopausal status before study enrollment.

### Contraception Guidance

#### Female participants

Female participants of childbearing potential are eligible to participate if they agree to use a highly effective method of contraception consistently and correctly as described in [Table 8](#).

**Table 8****Highly Effective Contraceptive Methods**

Highly Effective Contraceptive Methods That Are User Dependent a Failure rate of <1% per year when used consistently and correctly.	
Combined (estrogen- and progestogen-containing) hormonal contraception associated with inhibition of ovulation b	

 
• oral
 
• intravaginal
 
• transdermal
 
	
Progestogen-only hormonal contraception associated with inhibition of ovulation b	

 
• injectable
 
	
Highly Effective Methods That Are User Independent	

 
• Implantable progestogen-only hormonal contraception associated with inhibition of ovulationb
 
• Intrauterine device (IUD)
 
• Intrauterine hormone-releasing system (IUS)
 
• bilateral tubal occlusion
 
	
Vasectomized partner	

(A vasectomized partner is a highly effective contraception method provided that the partner is the sole male sexual partner of the WOCBP and the absence of sperm has been confirmed. If not, an additional highly effective method of contraception should be used.)
	
Sexual abstinence	

(Sexual abstinence is considered a highly effective method only if defined as refraining from heterosexual intercourse during the entire period of risk associated with the study drug. The reliability of sexual abstinence needs to be evaluated in relation to the duration of the study and the preferred and usual lifestyle of the participant.)
	

## NOTES:

- a. Typical use failure rates may differ from those when used consistently and correctly. Use should be consistent with local regulations regarding the use of contraceptive methods for participants in clinical studies.
- b. Hormonal contraception may be susceptible to interaction with the study drug, which may reduce the efficacy of the contraceptive method. In this case two highly effective methods of contraception should be utilized during the treatment period and for at least 60 hours after the last dose of study treatment

**Pregnancy Testing**

- WOCBP should only be included after a confirmed menstrual period and a negative highly sensitive urine or serum pregnancy test
- Pregnancy testing will be performed whenever a menstrual cycle is missed or when pregnancy is otherwise suspected

- Pregnancy testing, with a sensitivity of 5 mIU/mL will be performed using the test kit provided by the central laboratory and in accordance with instructions provided in its package insert.

## **Collection of Pregnancy Information**

### **Male participants with partners who become pregnant**

- Investigator will not routinely attempt to collect pregnancy information on any male participant's female partner(s) who becomes pregnant while the male participant is participating in this study; however, voluntary reports of such incidents will be captured through the GSK standard reporting mechanism. This applies only to male participants who receive double-blind study treatment.
- If pregnancy information for a male participant's female partner(s) is voluntarily reported, after obtaining the necessary signed informed consent from the pregnant female partner directly, the investigator will record pregnancy information on the appropriate form and submit it to GSK within 24 hours of learning of the partner's pregnancy.
- Partner will also be followed to determine the outcome of the pregnancy. Information on the status of the mother and child will be forwarded to GSK
- Generally, follow-up will be no longer than 6 to 8 weeks following the estimated delivery date. Any termination of the pregnancy will be reported regardless of fetal status (presence or absence of anomalies) or indication for procedure

### **Female Participants who become pregnant**

- Investigator will collect pregnancy information on any female participant, who becomes pregnant while participating in this study.
- Information will be recorded on the appropriate form and submitted to GSK within 24 hours of learning of a participant's pregnancy.
- Participant will be followed to determine the outcome of the pregnancy. The investigator will collect follow up information on participant and neonate, which will be forwarded to GSK. Generally, follow-up will not be required for longer than 6 to 8 weeks beyond the estimated delivery date.
- Any termination of pregnancy will be reported, regardless of fetal status (presence or absence of anomalies) or indication for procedure.
- While pregnancy itself is not considered to be an AE or SAE, any pregnancy complication or elective termination of a pregnancy will be reported as an AE or SAE.
- A spontaneous abortion is always considered to be an SAE and will be reported as such.
- Any SAE occurring as a result of a post-study pregnancy which is considered reasonably related to the study treatment by the investigator, will be reported to GSK

as described in [Appendix 4](#). While the investigator is not obligated to actively seek this information in former study participants, he or she may learn of an SAE through spontaneous reporting.

Any female participant who becomes pregnant while participating will be withdrawn from the study.

## 12.6. Appendix 6: Liver Safety: Required Actions and Follow-up Assessments

### Phase I liver chemistry stopping criteria and required follow up assessments

Liver Chemistry Stopping Criteria	
Required Actions and Follow up Assessments	
Actions	Follow Up Assessments

ALT-absolute
 
ALT<math>\geq</math>3xULN
 
If ALT<math>\geq</math>3xULN AND bilirubin <math>\geq</math> 2xULN (<math>>35\%</math> direct bilirubin) or INR <math>>1.5</math>, Report as an SAE.
 
See additional Actions and Follow Up Assessments listed below
	
 
Report the event to GSK within 24 hours
 
Complete the liver event CRF, and complete an SAE data collection tool if the event also meets the criteria for an SAE
 
Perform liver event follow up assessments
 
Monitor the subject until liver chemistries resolve, stabilise, or return to within baseline (see MONITORING below)
 
 
MONITORING:
 
If ALT<math>\geq</math>3xULN AND bilirubin <math>\geq</math> 2xULN or INR <math>>1.5</math>:
 
 
Repeat liver chemistries (include ALT, AST, alkaline phosphatase, bilirubin) and perform liver event follow up assessments within 24 hrs
 
Monitor subjects twice weekly until liver chemistries resolve, stabilise or return to within baseline
 
A specialist or hepatology consultation is recommended
 
 
If ALT<math>\geq</math>3xULN AND bilirubin <math><</math> 2xULN and INR <math>\leq 1.5</math>:
 
 
Repeat liver chemistries (include ALT, AST, alkaline phosphatase, bilirubin) and perform liver event follow up assessments within 24-72 hrs
 
 
If ALT<math>\geq</math>3xULN AND bilirubin <math>\geq</math> 2xULN or INR <math>>1.5</math>:
 
 
Anti-nuclear antibody, anti-smooth muscle
 

Liver Chemistry Stopping Criteria	

 
Monitor subjects weekly until liver chemistries resolve, stabilize or return to within baseline
 
	
antibody, Type 1 anti-liver kidney microsomal antibodies, and quantitative total immunoglobulin G (IgG) or gamma globulins.
 
 
Serum acetaminophen adduct high performance liquid chromatography (HPLC) assay (quantifies potential acetaminophen contribution to liver injury in subjects with definite or likely acetaminophen use in the preceding week [James, 2009]. NOTE: not required in China.
 
Liver imaging (ultrasound, magnetic resonance, or computerised tomography) and /or liver biopsy to evaluate liver disease; complete Liver Imaging and/or Liver Biopsy CRF forms.
 

1. Serum bilirubin fractionation should be performed if testing is available. If serum bilirubin fractionation is not immediately available, discontinue study treatment for that subject if  $ALT \geq 3 \times ULN$  and bilirubin  $\geq 2 \times ULN$ . Additionally, if serum bilirubin fractionation testing is unavailable, record presence of detectable urinary bilirubin on dipstick, indicating direct bilirubin elevations and suggesting liver injury.
2. All events of  $ALT \geq 3 \times ULN$  and bilirubin  $\geq 2 \times ULN$  ( $>35\%$  direct bilirubin) or  $ALT \geq 3 \times ULN$  and INR  $> 1.5$ , if INR measured, which may indicate severe liver injury (possible 'Hy's Law'), must be reported as an SAE (excluding studies of hepatic impairment or cirrhosis); INR measurement is not required and the threshold value stated will not apply to subjects receiving anticoagulants
3. Includes: Hepatitis A IgM antibody; Hepatitis B surface antigen and Hepatitis B Core Antibody (IgM); Hepatitis C RNA; Cytomegalovirus IgM antibody; Epstein-Barr viral capsid antigen IgM antibody (or if unavailable, obtain heterophile antibody or monospot testing); Hepatitis E IgM antibody

## 12.7. Appendix 7: Neutrophil Safety and Study Treatment Restart

Neutrophil Stopping Criteria: Absolute neutrophil count (ANC) $\leq 0.5 \times 10^9 / \text{L}$	
Required Actions and Follow up Assessments	
Actions	Follow Up Assessments

 
• Immediately discontinue study treatment
 
• Report the event to GSK within 24 hours
 
• Complete an SAE data collection tool if the event also meets the criteria for an SAE
 
• Monitor the participant until neutrophil count stabilizes or returns to within baseline (see MONITORING below)
 
• Do not restart participant with study treatment unless allowed per protocol and GSK Medical Governance approval is granted (see RESTART below)
 
 
MONITORING:
 
 
• Treatment of any suspected infections
 
• Repeat CBC within 24 hrs
 
• Monitor CBC daily until neutrophil count resolves, stabilizes or returns to within baseline
 
	
 
• Record the appearance or worsening of any clinical symptoms on the AE report form^1
 
• Obtain blood sample for pharmacokinetic (PK) analysis within 12 hours after last dose
 
• Record use of concomitant medications on the concomitant medications report form
 

RESTART	

 
• Restart of study medication must be approved by the GSK Medical Monitor
 
• Restart may be attempted ONLY if all three criteria are met: 
 
• The neutrophil count is <math>\geq 1.5 \times 10^9 / \text{L}</math> for at least 48 hours
 
• At least 7 days have elapsed since the suspension of study treatment
 
• No sign or symptom of associated infection has been identified
 
 
 
	
 
• Check the CBC within 24-48 hours after re-starting study medication, monitor twice weekly for two weeks, and monthly thereafter.
 
• If the ANC drops below <math>1.0 \times 10^9 / \text{L}</math> on restart, the participant should be permanently discontinued from study treatment and withdrawn from the study.
 

1. New or worsening symptoms believed to be related to neutropenia such as (but not limited to): sudden onset of fever or malaise, stomatitis, odynophagia, periodontal infection, skin abscesses, signs or symptoms of sinusitis and otitis, symptoms of pneumonia (eg, cough, dyspnea), perirectal pain and irritation, hypotension or signs of septic shock.

2. Record the date/time of the PK blood sample draw and the date/time of the last dose of study treatment prior to

PK blood sample draw on the CRF. If the date or time of the last dose is unclear, provide the participant's best approximation. If the date/time of the last dose cannot be approximated OR a PK sample cannot be collected in the time period indicated above, do not obtain a PK sample. Instructions for sample handling and shipping are in the SRM.

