Impairment of host defense.	
Host defense has not been studied directly in nonclinical studies. However, data in nonclinical species have not identified an increased risk of infection with danirixin. Nonclinical studies in mice and ferrets with two CXCR2 antagonists in the same chemical class as danirixin have not shown an increase in infections in challenge models (e.g., influenza viral load). Secondary bacterial infections after viral infection have not been directly evaluated in nonclinical studies.
 
The data from clinical studies including healthy participants, COPD and influenza patients thus far show no evidence that participants taking danirixin have an increased infection rate compared with participants taking placebo.
 
Neutropenia has been reported in clinical trials of other CXCR2 antagonists. No instances of neutropenia have been reported in nonclinical studies with danirixin. In
	
Monitoring of neutrophil count.
 
Stopping criteria: in participants with a confirmed absolute neutrophil count <math>\leq 0.5 \times 10^9/L</math> product will be discontinued and neutrophil count will be monitored until return to normal. Participants may be restarted on study treatment as detailed in Appendix 7.
 
Ongoing assessment of AE/SAEs related to infection.
 
Closely monitor, collect information on and characterize infection events such as pneumonia, and use adjudication as appropriate.

Investigational Product (IP) [Danirixin, GSK1325756]		
Potential Risk of Clinical Significance	Summary of Data/Rationale for Risk	Mitigation Strategy

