### 8.1.3. Neutrophil Stopping Criteria

A participant with a peripheral blood neutrophil count  $\leq 0.5 \times 10^9/L$  that is confirmed on repeat testing will be instructed to suspend dosing. The neutrophil count should be monitored daily until it returns to within the baseline value, as detailed in [Appendix 7](#).

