**Table 7 Protocol-Required Safety Laboratory Assessments**

Laboratory Assessments	Parameters			
Hematology	Platelet Count	RBC Indices: MCV MCH %Reticulocytes	WBC count with Differential: Neutrophils Lymphocytes Monocytes Eosinophils Basophils	
	RBC Count			
	Hemoglobin			
	Hematocrit			
Clinical Chemistry 	BUN	Potassium	Aspartate Aminotransferase (AST)/Serum Glutamic-Oxaloacetic Transaminase (SGOT)	Total and direct bilirubin
	Creatinine	Sodium	Alanine Aminotransferase (ALT)/ Serum Glutamic-Pyruvic Transaminase (SGPT)	Total Protein
	Glucose [fasting]	Calcium	Alkaline phosphatase,	Albumin
Routine Urinalysis	
 
• Specific gravity
 
• pH, glucose, protein, blood, ketones, bilirubin, urobilinogen, nitrite, leukocyte esterase by dipstick
 
• Microscopic examination (if blood or protein is abnormal)
 
			
Other Screening Tests	
 
• Follicle-stimulating hormone and estradiol (as needed in women of non-childbearing potential only)
 
• Breathalyzer alcohol screen and a urine drug screen to include at minimum: amphetamines, barbiturates, cocaine, opiates, cannabinoids and
 
			

Laboratory Assessments	Parameters
	
benzodiazepines.
 
 
• Serum or urine human chorionic gonadotropin (hCG) pregnancy test (as needed for women of childbearing potential) 
 
• Serology : HIV antibody, hepatitis B surface antigen [HBsAg], and hepatitis C virus antibody
 
 
 
 
The results of each test must be entered into the CRF.

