23.	mlTT	CP_LB6	Listing of All Haematology Laboratory Data for Subjects with Any Value of Potential Clinical Importance	ICH E3	SAC
24.	mlTT	CP_LB6	Listing of Clinical Chemistry Abnormalities of Potential Clinical Importance		SAC
25.	mlTT	CP_LB6	Listing of Haematology Abnormalities of Potential Clinical Importance		SAC
26.	mlTT	UR2A/UR2B	Listing of Urinalysis Data	ICH E3	SAC
ECG					
27.	mlTT	CP_EG4	Listing of All ECG Values for Subjects with Any Value of Potential Clinical Importance	IDSL	SAC
28.	mlTT	CP_EG4	Listing of ECG Values of Potential Clinical Importance	IDSL	SAC
29.	mlTT	CP_EG6	Listing of All ECG Findings for Subjects with an Abnormal ECG Finding	IDSL	SAC
30.	mlTT	CP_EG6	Listing of Abnormal ECG Findings	IDSL	SAC
Vital Signs					
31.	mlTT	CP_VS5	Listing of All Vital Signs Data for Subjects with Any Value of Potential Clinical Importance	IDSL	SAC
32.	mlTT	CP_VS5	Listing of Vital Signs of Potential Clinical Importance	IDSL	SAC

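### SAP 10.8.1 flags neutrophils only as a percentage although the protocol's neutrophil rules are absolute counts, so the haematology listings can miss a low count and list a normal one (minor reporting gap)

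*Protocol*

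**What the plan says.** **Protocol.** The neutrophil rules are stated in x10^9/L wherever they appear.

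- Section 3.3.1 treats neutropenia within the host-defence risk. The mitigation begins with "Monitoring of neutrophil count" and continues "Stopping criteria: in participants with a confirmed absolute neutrophil count" at or below 0.5.
- Section 8.1.3 applies to "A participant with a peripheral blood neutrophil count" at or below 0.5, confirmed on repeat testing.
- Appendix 7 gives the stopping criterion as "Absolute neutrophil count (ANC") at or below 0.5. Among its conditions for restart is "The neutrophil count is" at least 1.5 for 48 hours. After a restart, the rule beginning "If the ANC drops below" 1.0 leads to permanent discontinuation.
- Appendix 2, Table 7 collects the white cell count with its differential ("Neutrophils Lymphocytes Monocytes Eosinophils Basophils") and gives no unit for the differential.

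**SAP.** Section 10.8.1 has one neutrophil row, in per cent, with low 0.85x and high 1.50x. Total white cells have low 0.70x and high 1.60x. A note says that x marks a multiplier, but for haematology nothing says what is multiplied. Section 10.10.8 plans two haematology listings: Listing 23, which gives all haematology data for participants with any value of potential clinical importance, and Listing 25, "Listing of Haematology Abnormalities of Potential Clinical Importance". Section 10.5.2 leaves unscheduled visits out of summary tables and figures. Section 10.7.1 does the same for laboratory data from an early discontinuation visit. Both sections say that these data will be listed.

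**The concern.** A neutrophil percentage depends on the other white cells as well as on the neutrophils. If all white cells fall together, the percentage can stay near its limit while the absolute count is low. If lymphocytes rise, the percentage can fall while the count is normal. The flag therefore measures a different quantity from the one on which the protocol's rules are written.

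The flags matter because they decide who appears in Listings 23 and 25. No unconditional haematology listing is planned, so the SAP's promise to list unscheduled and early-discontinuation results is kept for haematology only when some haematology value has been flagged. Repeat counts would normally be unscheduled. The laboratory summaries in SAP 8.2 cover screening, baseline (Day -1 of the first period, SAP 5.2) and follow-up. Day -1 samples of later periods, drawn after earlier danirixin doses, are not named there, although the title of Table 3.8 refers to pre-dose values. What is at stake is whether the report describes neutrophil safety in the protocol's own terms, in a study where clinical laboratory parameters are a safety endpoint in both parts.

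**Working it through.** The plan gives no figure of its own to reproduce. The check asks how low an absolute neutrophil count (ANC) can be while neither the white cell (WBC) row nor the neutrophil row is flagged.

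**Inputs.** Multipliers 0.70 (WBC) and 0.85 (neutrophil %) are from SAP 10.8.1. Two assumptions are needed: that x multiplies the lower limit of normal (LLN), and the limits themselves, since the tests are run by a local laboratory whose ranges are not given. I take LLN WBC 4.0 x10^9/L (range 3.5-4.5) and LLN neutrophils 40% (range 35-50%).

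**Formula.** ANC = WBC x neutrophil % / 100. The lowest unflagged ANC is

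(0.70 x LLN WBC) x (0.85 x LLN % / 100) = 0.595 x LLN WBC x LLN % / 100.

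**Central case.** The cut-offs are WBC 0.70 x 4.0 = 2.80 and neutrophils 0.85 x 40 = 34%. The floor is 2.80 x 0.34 = 0.952 x10^9/L.

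**Range of assumed limits** (lowest unflagged ANC, x10^9/L):

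| LLN WBC | LLN 35% | LLN 40% | LLN 45% | LLN 50% |
|---|---|---|---|---|
| 3.5 | 0.729 | 0.833 | 0.937 | 1.041 |
| 4.0 | 0.833 | 0.952 | 1.071 | 1.190 |
| 4.5 | 0.937 | 1.071 | 1.205 | 1.339 |

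**A low count that is missed (central case).** WBC 2.9 with 35% neutrophils gives 2.9 x 0.35 = 1.015, and neither row is flagged. The window is narrow: an ANC of exactly 1.0 is unflagged only for WBC from 2.80 to 1.0 / 0.34 = 2.94.

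**A normal count that is flagged.** WBC 9.0 with 30% neutrophils gives 2.70. This is above the implied lower limit for the count (4.0 x 0.40 = 1.6), but it is flagged low because 30% is below 34%.

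**Selective neutrophil fall.** With other white cells fixed at m, a flag is raised when ANC < max(0.34 / 0.66 x m, 2.80 - m).

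- m = 1.9: max(0.98, 0.90) = 0.98
- m = 2.4: max(1.24, 0.40) = 1.24
- m = 4.5: the first term, 2.32, governs

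When only neutrophils fall, the flag therefore usually comes well above the floor.

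**The stopping threshold.** The smallest floor in the table is 0.729, so a count at or below 0.5 always raises a flag on this grid. For it to escape, LLN WBC x LLN % / 100 would have to be at most 0.5 / 0.595 = 0.84, and the smallest product on the grid is 3.5 x 0.35 = 1.23.

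**Limit of the check.** Only the WBC and neutrophil rows are used. A flag on any other haematology row would also bring the participant into Listing 23, so these floors are the lowest possible unlisted counts.

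**The case against.** **The threshold that matters is caught.** The only count that starts any neutrophil action is 0.5 or below, and it is always flagged under the assumed limits. This stands. A reader might infer that a stopping event could be missing from the listings; the arithmetic does not support that.

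**The values 1.0 and 1.5 are restart conditions.** In Appendix 7 both apply only to someone who has already stopped, so a first count of about 1.0 triggers no protocol rule. This stands too. A reader might take them as general low-count limits for every participant; the protocol does not give them that role.

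**Participants are protected by other routes.** The site applies the stopping rule to counts and reports to the sponsor within 24 hours. The investigator reviews each laboratory report (Protocol 9.4.4), and abnormalities judged clinically significant are adverse events (Appendix 4), which reach SAP Tables 3.1 and 3.6 and Listings 15 and 20 where they meet those displays' criteria. None of this uses the flags, so a reading that safety oversight is weakened is not supported. These routes depend on clinical judgement, however, and do not replace a numerical listing of low counts.

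**Over-listing does little harm.** Listing 23 shows all haematology data for a listed participant, so where WBC is shown beside the percentage the count can be worked out. This largely disposes of the normal-count half of the concern. It does not help a participant who is never listed.

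**The figure is unstable, and some sources are unseen.** The floor varies from 0.73 to 1.34 and needs both values at their cut-offs. Table 3.8 might already summarise absolute neutrophils under the sponsor's standards; the SAP does not say. Both points limit the size of the gap, but the missing row is plain in the text.

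**Conclusion.** The point holds as a minor reporting gap in SAP 10.8.1. The protocol's own text contains no error here. For a risk the protocol names (impairment of host defence, within which neutropenia is discussed), the SAP's flag measures a percentage where the protocol acts on a count, and the only haematology listings depend on such flags. A low absolute count above the stopping threshold can go unlisted, and if it was measured at an unscheduled or early-discontinuation visit it is left out of the summaries as well.

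The worst-case unflagged count is 0.95 x10^9/L at limits of 4.0 and 40%, and 0.73 to 1.34 over the range examined. These figures rest on assumed reference limits and on reading x as a multiple of the lower limit. The unit mismatch does not depend on either assumption. No pharmacokinetic result and no stopping decision is affected.

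**What to change.** In SAP 10.8.1:

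- Add a row for absolute neutrophil count in x10^9/L, taken as reported by the laboratory or derived as WBC x neutrophil % / 100.
- Give it a reporting flag that includes the protocol's criterion of 0.5 or below, and a low-count reporting limit above that, chosen by the sponsor. If 1.0 and 1.5 are shown, label them as restart conditions.
- State what x multiplies for haematology.
- Keep the percentage row.

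Use the new row for Listings 23 and 25, and include the absolute count in Table 3.8. With the new row, the example with WBC 2.9 and 35% neutrophils (1.015) would be listed if the sponsor's limit lies above that value, and the example with WBC 9.0 and 30% (2.70) would no longer look low on the count if the limit lies below 2.70.

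The cost is SAP wording and at most one derived variable. White cells and the differential are already collected, so this needs no new sample, no protocol amendment and no change to any clinical rule.
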